| | 
• Problem list of comorbidities (OSA, COPD, asthma, HTN, HLD, CAD, CHG, arrhythmia, pulmonary hypertension, DM (type 1 or 2), coagulopathy, hx of dvt/PE, anxiety, depression, bipolar disorder, schizophrenia, IBS)• Number of allergies• Pre-op medications: betablockers, asa, anticoagulant, NSAID, Opioid, steroids, ACE inhibitor, calcium antagonists and diuretics, blood pressure (pre-op and all intra-op), intra-op medication: TXA IV or topical, ketamine, blood transfusion, albumin, IV fluids, epinephrine, ephedrine, phenylephrine, hydralazine, labetalol,• Laboratory results: hemoglobin, BUN, creatinine (pre-op and first post-op)• Post-operative medications for the first 24 hours: IV fluids, albumin, blood transfusion, epinephrine, ephedrine, phenylephrine, opioids• Complications: MI, CVA, death, ARF, pneumonia, arrhythmia, DVT, PE |
| Statistical Analysis: | 
• Two-step logistic regression modeling to determine odds ratios• Confidence intervals: 95% |

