5.1.2 Secondary Endpoints

The secondary outcomes are incidences of:

- i. acute renal failure (ARF)
- ii. Pneumonia
- iii. Arrhythmia
- iv. deep venous thrombosis (DVT)
- v. pulmonary embolism (PE)
- vi. blood transfusion

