7.0 PROCEDURES

The independent variables of interest include extent of intraoperative hypotension (MAP <45, 50, 55, 60 mmHg) and duration of hypotension (5 mins interval). Intraoperative blood loss will be calculated based on pre-operative and post-operative laboratory hemoglobin levels.

The outcome variables include MI, CVA, death, intraoperative blood loss, ARF, pneumonia, arrhythmia, DVT, PE, and number of packed red blood cell (pRBC) transfusions.

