7.1 Data Collection

The following data will be collected:

Pre-operative/Baseline

- MRN
- Age
- Height
- Weight
- BMI
- ASA classification
- Ethnicity
- Gender
- Baseline status: METS, substance hx, smoking hx, SOB
- Comorbidity: OSA, COPD, asthma, HTN, CAD, CHF, Arrhythmia, pulmonary hypertension, seizure, TIA/CVA, renal dx, DM (type I or type II), coagulopathy, hx of dvt/PE
- Pre-op medications: beta-block, asa, anti-coagulant, nsaid, steroids
- Blood pressure: pre-op BP, and all intra-op

Intra-Operative

- Blood pressure: pre-op BP and all intra-op
- Intra-op medications: TXA IV or topical, ketamine, blood transfusion, albumin, IV fluids, epinephrine, ephedrine, phenylephrine, hydralazine, labetalol

Post-Operative

- Laboratory results: hemoglobin, BUN, creatinine

- Post-operative medications: (first 24 hours) IV fluids, albumin, blood transfusion, epinephrine, ephedrine, phenylephrine
- Complications: MI, CVA, death, ARF, pneumonia, arrhythmia, DVT, PE

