8.0 STATISTICAL ANALYSIS

1. Proposed analysis (e.g., student's t-test, ANOVA, chi-square, regression, etc.):
Two-step logistic regression modeling to determine odds ratios
2. Confidence intervals: 95%
3. Total sample size required: 10,000

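### Transfusion is an incidence in 5.1.2 but a count in 7.0, and post-operative collection stops at 24 hours, so a patient first transfused later is coded as not transfused

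*Combined protocol and SAP*

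**What the plan says.** Section 5.1.2 opens with "The secondary outcomes are incidences of" and gives "vi. blood transfusion" as its last item. No blood product, unit of counting or time window is attached to it. Section 7.0, in its list of outcome variables, has "number of packed red blood cell (pRBC) transfusions".

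Section 8.0 names one analysis: "Two-step logistic regression modeling to determine odds ratios". The synopsis says the same. Neither names a count or ordinal model, or a rule for turning a count into a yes/no outcome.

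Transfusion data enter the study by two routes. During surgery, 7.1 has "Intra-op medications: TXA IV or topical, ketamine, blood transfusion, albumin, IV fluids". After surgery, 7.1 has "Post-operative medications: (first 24 hours) IV fluids, albumin, blood transfusion, epinephrine, ephedrine, phenylephrine", and the synopsis agrees: "Post-operative medications for the first 24 hours: IV fluids, albumin, blood transfusion". The post-operative complications list, in both places, carries no 24-hour limit and does not include transfusion. Section 5.1.1 sets the inpatient stay as the window for the primary outcomes. No window is set for the secondary outcomes.

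**The concern.** There are two separate problems.

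The first is definition. One outcome appears on two scales (occurrence and number) and with two product scopes (unspecified and pRBC only). The outcomes of a retrospective record study already exist when the data are pulled. A choice that the plan leaves open can therefore be made after the results are seen.

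The second is capture, and it matters more. If the data are pulled as written, a patient who receives no blood in theatre or in the first 24 hours but is transfused on a later inpatient day appears in the dataset as a non-event. Nothing else in the collection list would reveal the error. Transfusion is the only secondary outcome treated this way, because the other five are drawn from the complications list, which has no such limit.

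At stake are the precision of the transfusion odds ratios and, if the timing of first transfusion varies with the depth or duration of hypotension, their validity.

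**Working it through.** **No figure to reproduce.** The plan gives no transfusion rate, transfusion timing, length of stay, effect size or power for this endpoint. The sample size of 10,000 is stated without a derivation, and this point does not depend on it.

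**Step 1: the definitions side by side.**

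| Feature | 5.1.2 | 7.0 |
|---|---|---|
| Scale | incidence (yes/no per patient) | number (0, 1, 2, ...) |
| Product | not specified | pRBC |
| Window | not specified | not specified |

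Binary logistic regression (8.0) fits the 5.1.2 column directly. It fits the 7.0 column only after a cut, such as number > 0, and the plan does not state one.

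**Step 2: the collection route.** Sources of transfusion data are intra-operative (yes), first 24 hours post-operative (yes), after 24 hours (none). The complications list omits transfusion, so it cannot fill the gap.

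**Step 3: who is lost.** For a yes/no endpoint, a patient transfused in theatre or within 24 hours counts as an event even if later units are missed. Only patients whose *first* transfusion falls after 24 hours are misclassified. The relevant quantity is therefore their share of all ever-transfused patients, not the share of transfusions given late. For a count endpoint, every transfusion after 24 hours would be lost.

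**Step 4: illustrative effect on precision.** Let s be the share of ever-transfused patients who are captured. When events are uncommon, the standard error of the log odds ratio is approximately √(1/a + 1/c), where a and c are the event counts in the two exposure groups. If capture is the same in both groups, a and c become s·a and s·c, and the standard error is multiplied by 1/√s.

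- Assumed 20% first transfused after 24 hours: s = 0.8, 1/√0.8 = 1.12.
- Assumed 50% first transfused after 24 hours: s = 0.5, 1/√0.5 = 1.41.

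The 20-50% range is an assumption; nothing in the documents supports or narrows it.

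**Step 5: bias.** With true risks p1 and p0 and capture shares s1 and s0, the observed risk ratio is (s1·p1)/(s0·p0). If s1 = s0, it equals the true ratio, and the odds ratio is nearly unchanged when events are uncommon. If s1 and s0 differ, the ratio is multiplied by s1/s0. The documents give no basis for the size or direction of any difference. The data as specified could not show one, because later transfusions are not pulled.

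**The case against.** The strongest reply is that nothing here is a contradiction. Section 5.1.2 is the endpoint section, it defines an incidence, and the stated model fits an incidence. A recorded number contains that incidence (any versus none), so 7.0 can stand beside 5.1.2 once a sentence links them. Surgery plus 24 hours is also a legitimate endpoint window, and no secondary-outcome window is stated for it to violate. Transfusion is one of six secondary outcomes, and Hypothesis B is worded in terms of calculated blood loss, not transfusion.

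Much of this stands, and it rules out several stronger readings that a reader might infer:

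- That the stated model cannot analyse transfusion at all. It can analyse the incidence, and the count if dichotomised.
- That 7.0 counts units. Its wording could mean units or episodes; either is a count.
- That the 24-hour limit contradicts a stated endpoint window. The inpatient-stay sentence in 5.1.1 covers primary outcomes only, so this is a gap in capture.
- That the cut biases the comparison in a known direction, for example through early haemodilution bringing transfusion forward. The documents give no transfusion trigger and do not link dilution to the exposure.

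The reply does not remove the capture gap. The plan nowhere presents 24 hours as the transfusion endpoint. The limit sits on an item that groups transfusion with fluids and vasopressors, which looks like a window for treatment data. A linking sentence would settle the scale but would not recover patients first transfused later in the stay.

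**Conclusion.** The point holds as a definition gap combined with a capture gap on a secondary endpoint. The mismatch between incidence and count is, taken alone, close to a missing detail. What makes the point worth acting on is that the data pull as written would record patients first transfused after 24 hours as not transfused, while the complication outcomes have no such cut-off.

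The loss cannot be derived from the documents. The illustrative widening of 1.12 to 1.41 rests on three assumptions: 20-50% of ever-transfused patients are first transfused after 24 hours, events are uncommon, and capture is the same across exposure levels. If few patients are first transfused late, the effect is small. Bias is a possibility, not a finding. The primary outcomes are unaffected by this point.

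**What to change.** 1. In 5.1.2 and 7.0, define the endpoint once: any pRBC transfusion (yes/no) from start of surgery to discharge, analysed by the logistic regression already stated in 8.0.
2. In the synopsis and 7.1, extend the transfusion item from the first 24 hours to the whole inpatient stay, and collect the date and time of each transfusion. The 24-hour limit on the other post-operative medications need not change.
3. Report a 24-hour version of the endpoint as a sensitivity analysis. Comparing the two will show how many patients are first transfused late and whether this differs by exposure.
4. Optionally, keep the number of transfusions as a supportive outcome. State whether it counts units or episodes, and name a suitable model such as negative binomial or proportional-odds regression.

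This is a cheap improvement. The cost is a wider query of the same electronic record and a few sentences of text, plus one further model if item 4 is taken up.

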7.1 Data Collection

The following data will be collected:

Pre-operative/Baseline

- MRN
- Age
- Height
- Weight
- BMI
- ASA classification
- Ethnicity
- Gender
- Baseline status: METS, substance hx, smoking hx, SOB
- Comorbidity: OSA, COPD, asthma, HTN, CAD, CHF, Arrhythmia, pulmonary hypertension, seizure, TIA/CVA, renal dx, DM (type I or type II), coagulopathy, hx of dvt/PE
- Pre-op medications: beta-block, asa, anti-coagulant, nsaid, steroids
- Blood pressure: pre-op BP, and all intra-op

Intra-Operative

- Blood pressure: pre-op BP and all intra-op
- Intra-op medications: TXA IV or topical, ketamine, blood transfusion, albumin, IV fluids, epinephrine, ephedrine, phenylephrine, hydralazine, labetalol

Post-Operative

- Laboratory results: hemoglobin, BUN, creatinine

- Post-operative medications: (first 24 hours) IV fluids, albumin, blood transfusion, epinephrine, ephedrine, phenylephrine
- Complications: MI, CVA, death, ARF, pneumonia, arrhythmia, DVT, PE

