Outcomes after Hypotensive Neuraxial Anesthesia in Total Hip Arthroplasty

FUNDER: Department of Anesthesiology

PROTOCOL NO.: 2018-2235

VERSION & DATE: 12/5/2018

TABLE OF CONTENTS

| | |
|---|----------|
| TABLE OF CONTENTS | 2 |
| PROTOCOL SYNOPSIS | 3 |
| 2.0 INTRODUCTION..... | 5 |
| 3.0 OBJECTIVE(S) OF CLINICAL STUDY | 5 |
| 4.0 STUDY HYPOTHESES | 6 |
| 5.0 STUDY DESIGN | 6 |
| 5.1 Endpoints | 6 |
| 5.1.1 Primary Endpoint | 6 |
| 5.1.2 Secondary Endpoints..... | 6 |
| 5.2 Study Sites | 6 |
| 6.0 STUDY POPULATION | 6 |
| 6.1 Number of Subjects..... | 6 |
| 6.2 Inclusion Criteria..... | 7 |
| 6.3 Exclusion Criteria | 7 |
| 7.0 PROCEDURES..... | 7 |
| 7.1 Data Collection | 7 |
| 8.0 STATISTICAL ANALYSIS..... | 8 |
| 9.0 ADVERSE EVENT ASSESSMENT | 8 |

PROTOCOL SYNOPSIS

| | |
|--------------------------------|--|
| Protocol Title: | Outcomes after Hypotensive Neuraxial Anesthesia in Total Hip Arthroplasty |
| Protocol Number: | 2018-2235 |
| Protocol Date: | |
| Sponsor: | Department of Anesthesiology |
| Principal Investigator: | [name], PhD |
| Objective: | The proposed project will be the largest study on deliberate hypotensive neuraxial anesthesia and adverse outcome in THA. It will provide essential feedback and guidance to our clinical practice, indicating whether we need to modify our intraoperative management for better patient outcomes and less adverse complications, or conversely may allow us to argue that deliberate hypotensive neuraxial anesthesia is not associated with adverse events. This will be the first significant database study to examine the clinical outcomes of patients undergoing THA with a deliberative hypotensive neuraxial anesthetic technique. |
| Study Design: | Retrospective study |
| Enrollment: | 10,000 |
| Subject Criteria: | All primary THA patient data with sufficiently complete intraoperative vital signs will be included in the study. |
| Data Collection: | Sources: Medical record Variables: 
• MRN• Age• BMI• ASA status• Ethnicity• Gender/sex• zip code• insurance• type of surgery• primary anesthetic type• anesthetic procedures• anesthesia provider name• anesthesia provider helpers (CRNA, Resident, Fellow)• surgeon• duration of surgery• duration of anesthesia |

| | |
|------------------------------|--|

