6.2 Inclusion Criteria

All primary THA patient data with sufficiently complete intraoperative vital signs will be included in the study.

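### Implant fixation (cemented, hybrid, uncemented) is a plausible confounder that neither data list names, so the plan cannot adjust for it directly; the size and direction of any bias are unknown.

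*Combined protocol and SAP*

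**What the plan says.** **Data collected.** In section 7.1 the intra-operative items are blood pressure and "Intra-op medications: TXA IV or topical, ketamine, blood transfusion, albumin, IV fluids, epinephrine, ephedrine, phenylephrine, hydralazine, labetalol". The synopsis list has some surgical fields that 7.1 lacks: "type of surgery", which is not defined, and "surgeon• duration of surgery• duration of anesthesia". Neither list names cement, fixation or implant. Both contain the medical record number.

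**Who is included.** Section 6.2 reads "All primary THA patient data with sufficiently complete intraoperative vital signs will be included in the study". Section 6.3 removes revision cases, anterior cases and incomplete vital signs. Nothing restricts fixation.

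**Exposure.** Section 7.0 defines it as "extent of intraoperative hypotension (MAP <45, 50, 55, 60 mmHg) and duration of hypotension (5 mins interval". The cause and timing of a fall in pressure play no part.

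**Outcomes.** Section 7.0 continues: "The outcome variables include MI, CVA, death, intraoperative blood loss, ARF, pneumonia, arrhythmia, DVT, PE", and adds red-cell transfusion.

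**Analysis.** Section 8.0 names a two-step logistic regression, 95% intervals and 10,000 patients. It lists no adjustment covariates.

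**The concern.** Section 3.0 presents the open question as deliberate, controlled hypotension against hypotension that is inadvertent or uncontrolled. A fall in pressure at cement insertion would be of the second kind, yet under section 7.0 it counts the same as a deliberate one.

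That cementing can lower MAP, and can separately lead to embolism, arrhythmia or death, is general clinical knowledge and is not in the documents. So are the ideas that it is used more in older patients and that it changes bleeding. If these hold at this hospital, fixation is a common cause of exposure and outcome. It is a surgical choice, not a consequence of the measured MAP, so it is a legitimate adjustment variable.

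The bias could run either way. If cementing lowers MAP, cement-related events collect in the low-MAP groups and hypotension looks harmful. If teams hold pressure higher when cement is planned, those events collect in the comparison group and hypotension looks safe. Hypothesis A in section 4.0 is one of no association, and section 3.0 intends the result to guide practice, so an error in either direction matters.

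**Working it through.** **Figures in the plan.** The only design figure is the 10,000 patients. It cannot be reproduced, because no event rate, effect size, power or exposure split is given. This point does not depend on it.

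**Inputs, all assumed.** The documents say nothing about how often cement is used or what it does.
- c, the cemented share of all cases: 5%, 10%, 20%.
- a and b, the proportions with MAP below 45 in cemented and in other cases: 40% and 20%, or reversed in direction, 12% and 20%.
- R, the risk ratio of cement for the outcome: 2, 3, 5.
- True risk ratio of hypotension: 1.

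**Formulas.**
- Exposed share: P = c·a + (1 − c)·b
- Cemented share among exposed: p1 = c·a / P
- Cemented share among unexposed: p0 = c·(1 − a) / (1 − P)
- Apparent risk ratio: [1 + p1(R − 1)] / [1 + p0(R − 1)]

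**Example, cement lowers MAP** (c = 0.10, a = 0.40, b = 0.20, R = 3). P = 0.04 + 0.18 = 0.22; p1 = 0.04/0.22 = 0.182; p0 = 0.06/0.78 = 0.077. Apparent risk ratio = 1.364/1.154 = 1.18.

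**Example, pressure kept higher with cement** (c = 0.20, a = 0.12, b = 0.20, R = 5). P = 0.024 + 0.160 = 0.184; p1 = 0.024/0.184 = 0.130; p0 = 0.176/0.816 = 0.216. Apparent risk ratio = 1.522/1.863 = 0.82.

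**Apparent risk ratio when the truth is 1:**

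| Cemented share | 40% vs 20% below 45: R = 2, 3, 5 | 12% vs 20% below 45: R = 2, 3, 5 |
|---|---|---|
| 5% | 1.06, 1.11, 1.20 | 0.98, 0.96, 0.92 |
| 10% | 1.10, 1.18, 1.32 | 0.96, 0.92, 0.87 |
| 20% | 1.15, 1.27, 1.43 | 0.93, 0.88, 0.82 |

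**Where it vanishes.** If a = b, then p1 = p0 and the ratio is 1.00 for any R. With cement rare and nearly balanced (3% of exposed, 2% of unexposed, R = 2) it is 1.03/1.02 = 1.01.

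**Against sampling error.** Take 22% of 10,000 exposed (2,200 against 7,800) and an assumed event risk of 0.2%: 4.4 and 15.6 expected events. The standard error of the log risk ratio is about √(1/4.4 + 1/15.6) = 0.54, so the 95% interval runs a factor of exp(1.96 × 0.54) ≈ 2.9 either side. At 0.5% risk there are 11 and 39 events, a standard error of 0.34 and a factor of about 1.9 to 2.0.

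**Limits.** These are crude ratios, before adjustment for anything. Section 8.0 reports odds ratios, which are close to risk ratios only for rare outcomes. The calculation does not apply to blood loss as a continuous measure.

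**The case against.** **Unsupported mechanism.** The documents never mention cement, so a reader who concludes that its effect *will* be read as an effect of hypotension goes too far. If few hips are cemented, or fixation is balanced across MAP groups, there is little or no bias. This stands: the point is about a possible bias that the listed fields do not let the study adjust for directly.

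**Collected variables cover part of it.** Section 7.1 has age, ASA class, METS, BMI, heart and lung disease and prior DVT or PE. If modelled, these would absorb part of any selection of older or sicker patients for cement. This also stands, but they would not capture a direct effect of cementing on pressure or embolism, and section 8.0 does not say that they will be modelled.

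**The exposure dilutes a brief dip.** Section 2.0 says many anesthesiologists here routinely run MAP at 40–60 mmHg, and exposure also has a duration in 5-minute steps. Much of the exposure is therefore deliberate, and a short fall adds little time. This makes 40% against 20% a less likely scenario, but a short fall still counts towards the threshold part of the exposure.

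**Proxies and linkage exist.** A reader might infer that the bias can be neither removed nor checked. That is too strong: the synopsis lists surgeon and duration of surgery, its surgery-type field could be defined to include fixation, and the record number may allow linkage to implant records. As written, though, surgeon and duration are only indirect proxies, and all three surgical fields are absent from 7.1.

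**Sampling error is larger.** For rare outcomes a distortion of 0.8 to 1.4 lies well inside the intervals worked out above. This is correct and bears on the fix: every added term has a cost when events are few. It does not excuse omitting the field, since bias does not shrink with more patients, and arrhythmia and blood loss may be estimated more precisely.

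**No adjustment set at all.** Section 8.0's silence on covariates is the more basic gap. Agreed: collecting fixation helps only if its use is also stated.

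**Conclusion.** The point holds as a plausible, unlisted confounder. Neither list names fixation, cemented hips are eligible, and the exposure does not separate causes of low MAP. With the fields as listed, the study could not adjust for fixation directly or show that it is balanced.

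The size and direction are unknown. A true null could appear as a risk ratio of about 0.8 to 1.4, but that range rests wholly on the assumed cement use, exposure pattern and cement risk, and on no other adjustment. It includes no bias. The outcomes most plausibly affected are death, PE, arrhythmia and blood loss. The mechanism described gives no clear route to CVA, so a claim that all the primary outcomes are distorted would not be supported. This is an inexpensive improvement worth making, not a demonstrated bias.

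**What to change.** 1. Add fixation (cemented, hybrid, uncemented) to the synopsis list and to section 7.1, or define the synopsis surgery-type field to include it and carry that field into 7.1.
2. In section 8.0, name fixation in the adjustment set for the blood-loss, arrhythmia and PE models.
3. For death, MI and CVA, where events are likely to be few, use a penalised model or repeat the analysis in uncemented cases only, as a sensitivity analysis. Do not force an extra term into an ordinary logistic model.
4. Tabulate fixation by MAP category. If it is balanced, or cement is rare, the report can say so and the matter is closed.

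The cost is one more field in a retrospective extraction and slightly less precision in the uncemented-only analysis, which drops the cemented patients.

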8.0 STATISTICAL ANALYSIS

1. Proposed analysis (e.g., student's t-test, ANOVA, chi-square, regression, etc.):
Two-step logistic regression modeling to determine odds ratios
2. Confidence intervals: 95%
3. Total sample size required: 10,000

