2.0 INTRODUCTION

There have been long debates in regards to the appropriate blood pressure management during joint replacement. Traditionally at HSS, many anesthesiologists routinely manage the blood pressure in the 40-60 mmHg MAP range to minimizing perioperative bleeding and optimize surgical outcome. Such deliberate hypotension anesthesia does not seem to cause increased risk of major complications in several studies, including studies from our institution (Paul et al, Can J Anesth 2007; Bombardieri et al, Anesth Analg, 2016; Weinstein et al. RAPM, 2018).

However, concerns still remain due to evidence from other major studies, which indicated increased complication risks with intraoperative hypotension (Salmasi et al, Anesthesiology, 2017; Sessler et al, Anesthesiology, 2018). Previous studies at HSS are mostly limited by the small number of patients, and therefore could not draw more convincing conclusion. With the implementation of EPIC electronic medical record system at HSS in 2016, it is feasible to access thousands of patients' intra-operative data nowadays. Hereby, we propose this project to study whether there is associated between deliberate hypotension and increased adverse outcomes among primary THA patients. In addition, we will explore whether controlled hypotension continues to be an effective technique for reducing intra-operative blood loss with modern surgical techniques and in the setting of widespread use of tranexamic acid.

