3.0 OBJECTIVE(S) OF CLINICAL STUDY

The goal of this study is to determine if hypotensive neuraxial anesthesia is associated with worse outcomes in Primary Total Hip Arthroplasty (THA). There is a substantial body of literature supporting the safety and utility of the practice of deliberate neuraxial hypotension for reduction of blood loss during THA. However, substantial controversy remains regarding the safety of deliberate and controlled intraoperative hypotension with epinephrine mediated cardiac output augmentation as compared to inadvertent and/or uncontrolled intraoperative hypotension. Moreover, it is unclear if advances in surgical practice combined with the widespread use of TXA have diminished the clinical utility of deliberate hypotension as a means of minimizing blood loss. Therefore, this study is looking at the extent and duration of hypotension under neuraxial anesthesia in primary THA surgery.

This proposed project will be the largest study on deliberative hypotensive neuraxial anesthesia and adverse outcome in total hip arthroplasty. It will provide essential feedback and guidance to our clinical practice, indicating whether we need to modify our intra-operative management for better patient outcomes and less adverse complications, or conversely may allow us to argue that deliberate hypotensive neuraxial anesthesia is not associated with adverse events.

We will be accessing and reviewing EPIC data of patients who have undergone Primary Total Hip Arthroplasty at HSS from January 2016- December 3, 2018

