4.0 STUDY HYPOTHESES

This is retrospective study hypothesize that:

- A. There is no association between level and duration of hypotension with (i) myocardial infarction (MI), (ii) cerebrovascular accident (CVA), (iii) death in primary total hip arthroplasty patients.
- B. With the use of IV tranexamic acid is administered, the use of deliberate neuraxial anesthesia induced hypotension does not result in a further clinically relevant reduction in calculated blood loss after total hip arthroplasty.

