5.0 STUDY DESIGN

5.1 Endpoints

5.1.1 Primary Endpoint

The primary outcomes are the incidences of:

- i. myocardial infarction (MI)
- ii. cerebrovascular accident (CVA)
- iii. death
- iv. calculated perioperative intraoperative blood loss.

All primary outcomes are events during the inpatients stay.

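### The only analysis named, logistic regression with odds ratios, cannot estimate the reduction in calculated blood loss that Hypothesis B concerns, and neither a cut-off nor a margin is stated

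*Combined protocol and SAP*

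**What the plan says.** Section 8.0 contains one method, "Two-step logistic regression modeling to determine odds ratios", a 95% confidence level and a total of 10,000 patients. The Statistical Analysis row of the synopsis repeats the method in the same words. The t-test, ANOVA and chi-square in Section 8.0 are examples inside the form's prompt, not planned analyses.

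Section 4.0 states two hypotheses. Hypothesis A concerns MI, CVA and death. Hypothesis B says that, when IV TXA is given, hypotension "does not result in a further clinically relevant reduction in calculated blood loss after total hip arthroplasty".

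Section 5.1.1 opens its list with "The primary outcomes are the incidences of" and gives four items: MI, CVA, death and "calculated perioperative intraoperative blood loss". It adds: "All primary outcomes are events during the inpatients stay".

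Section 7.0 derives blood loss from hemoglobin before and after surgery. The synopsis gives the sampling: "Laboratory results: hemoglobin, BUN, creatinine (pre-op and first post-op". Section 7.0 also defines the exposure, as MAP below 45, 50, 55 or 60 mmHg and duration in 5-minute intervals.

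No section gives a model for a continuous outcome, a blood-loss formula or unit, a cut-off that would turn blood loss into an event, or a value for clinical relevance.

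**The concern.** Hypothesis B claims that there is no relevant difference in an amount. To support it, the analysis must estimate that amount and show that its confidence interval excludes a reduction large enough to matter. The plan names a method whose effect measure is not an amount, and it sets no threshold for what matters.

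Two things are at stake. First, a non-significant odds ratio could be read as support for Hypothesis B. Second, the data are already recorded: Section 3.0 takes patients up to December 3, 2018, and the protocol is dated 12/5/2018. A model, cut-off or margin not fixed in writing could be chosen after results are seen. Section 3.0 says the findings should guide practice and asks whether surgical advances and TXA have "diminished the clinical utility of deliberate hypotension as a means of minimizing blood loss", so the blood-loss answer is meant to be used.

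**Working it through.** **The plan's own figure.** The total of 10,000 cannot be reproduced or refuted. The documents give no power, effect size, SD, event rate, exposure split or margin.

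**Matching method to outcome.**
- MI, CVA, death, ARF, pneumonia, arrhythmia, DVT, PE and any transfusion are yes/no outcomes. Logistic regression fits.
- Calculated blood loss is continuous, and Hypothesis B asks for the size of a reduction. An odds ratio does not estimate this.
- The MAP thresholds and 5-minute intervals in Section 7.0 define the exposure, so they do not supply a blood-loss cut-off.

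**What an odds ratio would say if blood loss were dichotomised.** All inputs here are assumptions: normally distributed blood loss, SD 300 to 700 mL, no covariate adjustment. Let d be the reduction divided by the SD, and put the cut at comparator quantile q, with normal score z_q. Then

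p1 = 1 − Φ(z_q + d), and OR = [p1/(1 − p1)] / [(1 − q)/q].

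*From odds ratio to volume.* At a median cut (q = 0.5), OR 0.73 gives p1 = 0.73/1.73 = 0.422, so d = 0.197. Multiplying by the SD:

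| Assumed SD (mL) | Reduction (mL) |
|---|---|
| 300 | 59 |
| 500 | 98 |
| 700 | 138 |

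*From volume to odds ratio.* A 100 mL reduction at SD 500 is d = 0.2:

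| Cut at comparator | OR |
|---|---|
| Median | 0.726 |
| 80th percentile | 0.699 |
| 90th percentile | 0.669 |

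One odds ratio therefore fits several volumes, and one volume gives several odds ratios.

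**What a mean difference would give.** The 95% half-width is 1.96 × SD × √[1/(ns) + 1/(n(1 − s))], where n is the number of IV-TXA patients and s the share in one exposure group. Both are assumed, since the documents give neither.
- n = 9,000: from 1.96 × 300 × √(1/4,500 + 1/4,500) = 12.4 mL to 1.96 × 700 × √(1/8,550 + 1/450) = 66.4 mL.
- n = 5,000: from 1.96 × 300 × √(1/2,500 + 1/2,500) = 16.6 mL to 1.96 × 700 × √(1/4,750 + 1/250) = 89.0 mL.

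These widths are in mL and can be compared directly with a margin. They describe sampling precision only, not confounding.

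**Why a margin is needed even with the right model.** With all 10,000 patients split 50:50, the difference detectable with 80% power at two-sided 0.05 is (1.96 + 0.84) × √(1/5,000 + 1/5,000) = 0.056 SD, or about 17 to 39 mL for SD 300 to 700. A significant result could be too small to matter. With fewer patients or an uneven split, a non-significant one could leave a larger reduction open. Significance alone settles neither case.

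**The case against.** **Blood loss is secondary in spirit.** Section 2.0 introduces it with "In addition, we will explore whether controlled hypotension continues to be an effective technique for reducing intra-operative blood loss", and the goal in Section 3.0 is framed around worse outcomes. This is fair, and the analysis of MI, CVA and death is unaffected. But Section 4.0 makes blood loss one of two hypotheses and Section 5.1.1 one of four primary outcomes, so it needs a stated analysis.

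**Section 8.0 may simply be silent on blood loss.** The plan does not map its one method to particular outcomes. A reader might infer, from the description of all primary outcomes as incidences and events, that blood loss will be dichotomised and put through the logistic model. The documents do not say so. The supported statement is that the one named method cannot answer Hypothesis B and no other is given. The odds-ratio figures above apply only if dichotomisation is meant.

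**A mean difference can also be imprecise.** This stands. With no observed effect and SD 500 mL, the reduction still compatible with the data would be about 26 mL for a median-cut odds ratio against 20.7 mL for a mean difference (9,000 patients, 50:50), and about 80 against 63.6 mL (5,000 patients, 95:5). Moving the second case to a 90th-percentile cut raises 80 to about 105 mL, but no section suggests that cut. A reader might take 26 to 105 mL as the harm done by odds ratios; most of that range comes from the assumed sample size and split. The case against the odds ratio is that it does not identify a volume.

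**TXA route.** Section 7.1 records IV or topical use, and a reader might infer a further gap for topical-only patients. Hypothesis B is limited to IV TXA, so they already fall outside it.

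**Conclusion.** The point holds and should be fixed before data extraction. The only named analysis does not estimate the quantity in Hypothesis B and primary outcome iv, and no margin exists against which to judge an estimate. This follows from the text and depends on no assumed number.

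The illustration of size, an odds ratio of 0.73 covering roughly 59 to 138 mL, rests on assumed normality, a median cut and SDs of 300 to 700 mL; none of these comes from the documents.

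The defect is confined to blood loss. A reader might conclude that logistic regression is wrong for the study as a whole, or that 10,000 patients are too few. The documents support neither: the method suits the binary outcomes, and adequacy of the sample cannot be judged without a margin, an SD and an exposure split.

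**What to change.** In Section 8.0 and the synopsis:

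1. Keep logistic regression for MI, CVA, death and the other binary outcomes, and say that it applies to those.
2. For Hypothesis B, specify a multivariable linear model with robust standard errors for calculated blood loss in mL. State the formula, based on pre-operative and first post-operative hemoglobin. Do not leave open a change to a log scale if the data look skewed: that choice would depend on the data, and the result would be a ratio rather than a difference in mL.
3. Fix the hypotension term in advance, using the extents and durations in Section 7.0. Either one primary contrast or a graded exposure term would serve.
4. Estimate the effect among IV-TXA patients, or through a hypotension-by-TXA term, and report the adjusted mean difference with its 95% CI.
5. State and justify, before data extraction, the smallest reduction in mL that counts as clinically relevant. Conclude that there is no further relevant reduction only if the CI excludes it.
6. Reword Section 5.1.1 so that blood loss is not listed as an incidence or event.

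The cost is one extra standard model, some text, and a margin that has to be justified. No new patients or variables are needed: the synopsis and Section 7.0 provide for hemoglobin before and after surgery (Section 7.1 lists it only post-operatively and should be aligned), and Section 7.1 lists height, weight, gender, transfusion and TXA route.
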